## **APPENDIX C: Declaration of Helsinki**

### **WORLD MEDICAL ASSOCIATION - DECLARATION OF HELSINKI**

#### **Ethical Principles for Medical Research Involving Human Subjects**

Adopted by the 18th WMA General Assembly, Helsinki, Finland, June 1964  
and amended by:

29th WMA General Assembly, Tokyo, Japan, October 1975

35th WMA General Assembly, Venice, Italy, October 1983

41st WMA General Assembly, Hong Kong, September 1989

48th WMA General Assembly, Somerset West, Republic of South Africa, October 1996

52nd WMA General Assembly, Edinburgh, Scotland, October 2000

53rd WMA General Assembly, Washington DC, USA, October 2002 (Note of Clarification  
added)

55th WMA General Assembly, Tokyo, Japan, October 2004 (Note of Clarification added)

59th WMA General Assembly, Seoul, Republic of Korea, October 2008

64th WMA General Assembly, Fortaleza, Brazil, October 2013

### **Preamble**

1. The World Medical Association (WMA) has developed the Declaration of Helsinki as a statement of ethical principles for medical research involving human subjects, including research on identifiable human material and data.

The Declaration is intended to be read as a whole and each of its constituent paragraphs should be applied with consideration of all other relevant paragraphs.

2. Consistent with the mandate of the WMA, the Declaration is addressed primarily to physicians. The WMA encourages others who are involved in medical research involving human subjects to adopt these principles.

### **General Principles**

3. The Declaration of Geneva of the WMA binds the physician with the words, "The health of my patient will be my first consideration," and the International Code of Medical Ethics declares that, "A physician shall act in the patient's best interest when providing medical care."

4. It is the duty of the physician to promote and safeguard the health, well-being and rights of patients, including those who are involved in medical research. The physician's knowledge and conscience are dedicated to the fulfilment of this duty.

5. Medical progress is based on research that ultimately must include studies involving human subjects.

6. The primary purpose of medical research involving human subjects is to understand the causes, development and effects of diseases and improve preventive, diagnostic and

therapeutic interventions (methods, procedures and treatments). Even the best proven interventions must be evaluated continually through research for their safety, effectiveness, efficiency, accessibility and quality.

7. Medical research is subject to ethical standards that promote and ensure respect for all human subjects and protect their health and rights.

8. While the primary purpose of medical research is to generate new knowledge, this goal can never take precedence over the rights and interests of individual research subjects.

9. It is the duty of physicians who are involved in medical research to protect the life, health, dignity, integrity, right to self-determination, privacy, and confidentiality of personal information of research subjects. The responsibility for the protection of research subjects must always rest with the physician or other health care professionals and never with the research subjects, even though they have given consent.

10. Physicians must consider the ethical, legal and regulatory norms and standards for research involving human subjects in their own countries as well as applicable international norms and standards. No national or international ethical, legal or regulatory requirement should reduce or eliminate any of the protections for research subjects set forth in this Declaration.

11. Medical research should be conducted in a manner that minimizes possible harm to the environment.

12. Medical research involving human subjects must be conducted only by individuals with the appropriate ethics and scientific education, training and qualifications. Research on patients or healthy volunteers requires the supervision of a competent and appropriately qualified physician or other health care professional.

13. Groups that are underrepresented in medical research should be provided appropriate access to participation in research.

14. Physicians who combine medical research with medical care should involve their patients in research only to the extent that this is justified by its potential preventive, diagnostic or therapeutic value and if the physician has good reason to believe that participation in the research study will not adversely affect the health of the patients who serve as research subjects.

15. Appropriate compensation and treatment for subjects who are harmed as a result of participating in research must be ensured.

## **Risks, Burdens and Benefits**

16. In medical practice and in medical research, most interventions involve risks and burdens.

Medical research involving human subjects may only be conducted if the importance of the objective outweighs the risks and burdens to the research subjects.

17. All medical research involving human subjects must be preceded by careful assessment of predictable risks and burdens to the individuals and groups involved in the research in comparison with foreseeable benefits to them and to other individuals or groups affected by the condition under investigation.

Measures to minimize the risks must be implemented. The risks must be continuously monitored, assessed and documented by the researcher.

18. Physicians may not be involved in a research study involving human subjects unless they are confident that the risks have been adequately assessed and can be satisfactorily managed.

When the risks are found to outweigh the potential benefits or when there is conclusive proof of definitive outcomes, physicians must assess whether to continue, modify or immediately stop the study.

### **Vulnerable Groups and Individuals**

19. Some groups and individuals are particularly vulnerable and may have an increased likelihood of being wronged or of incurring additional harm.

All vulnerable groups and individuals should receive specifically considered protection.

20. Medical research with a vulnerable group is only justified if the research is responsive to the health needs or priorities of this group and the research cannot be carried out in a non-vulnerable group. In addition, this group should stand to benefit from the knowledge, practices or interventions that result from the research.

### **Scientific Requirements and Research Protocols**

21. Medical research involving human subjects must conform to generally accepted scientific principles, be based on a thorough knowledge of the scientific literature, other relevant sources of information, and adequate laboratory and, as appropriate, animal experimentation. The welfare of animals used for research must be respected.

22. The design and performance of each research study involving human subjects must be clearly described and justified in a research protocol.

The protocol should contain a statement of the ethical considerations involved and should indicate how the principles in this Declaration have been addressed. The protocol should include information regarding funding, sponsors, institutional affiliations, potential conflicts of interest, incentives for subjects and information regarding provisions for treating and/or

compensating subjects who are harmed as a consequence of participation in the research study.

In clinical trials, the protocol must also describe appropriate arrangements for post-trial provisions.

### **Research Ethics Committees**

23. The research protocol must be submitted for consideration, comment, guidance and approval to the concerned research ethics committee before the study begins. This committee must be transparent in its functioning, must be independent of the researcher, the sponsor and any other undue influence and must be duly qualified. It must take into consideration the laws and regulations of the country or countries in which the research is to be performed as well as applicable international norms and standards but these must not be allowed to reduce or eliminate any of the protections for research subjects set forth in this Declaration.

The committee must have the right to monitor ongoing studies. The researcher must provide monitoring information to the committee, especially information about any serious adverse events. No amendment to the protocol may be made without consideration and approval by the committee. After the end of the study, the researchers must submit a final report to the committee containing a summary of the study's findings and conclusions.

### **Privacy and Confidentiality**

24. Every precaution must be taken to protect the privacy of research subjects and the confidentiality of their personal information.

### **Informed Consent**

25. Participation by individuals capable of giving informed consent as subjects in medical research must be voluntary. Although it may be appropriate to consult family members or community leaders, no individual capable of giving informed consent may be enrolled in a research study unless he or she freely agrees.

26. In medical research involving human subjects capable of giving informed consent, each potential subject must be adequately informed of the aims, methods, sources of funding, any possible conflicts of interest, institutional affiliations of the researcher, the anticipated benefits and potential risks of the study and the discomfort it may entail, post-study provisions and any other relevant aspects of the study. The potential subject must be informed of the right to refuse to participate in the study or to withdraw consent to participate at any time without reprisal. Special attention should be given to the specific information needs of individual potential subjects as well as to the methods used to deliver the information.

After ensuring that the potential subject has understood the information, the physician or another appropriately qualified individual must then seek the potential subject's freely-given informed consent, preferably in writing. If the consent cannot be expressed in writing, the non-written consent must be formally documented and witnessed.

All medical research subjects should be given the option of being informed about the general outcome and results of the study.

27. When seeking informed consent for participation in a research study the physician must be particularly cautious if the potential subject is in a dependent relationship with the physician or may consent under duress. In such situations the informed consent must be sought by an appropriately qualified individual who is completely independent of this relationship.

28. For a potential research subject who is incapable of giving informed consent, the physician must seek informed consent from the legally authorized representative. These individuals must not be included in a research study that has no likelihood of benefit for them unless it is intended to promote the health of the group represented by the potential subject, the research cannot instead be performed with persons capable of providing informed consent, and the research entails only minimal risk and minimal burden.

29. When a potential research subject who is deemed incapable of giving informed consent is able to give assent to decisions about participation in research, the physician must seek that assent in addition to the consent of the legally authorised representative. The potential subject's dissent should be respected.

30. Research involving subjects who are physically or mentally incapable of giving consent, for example, unconscious patients, may be done only if the physical or mental condition that prevents giving informed consent is a necessary characteristic of the research group. In such circumstances the physician must seek informed consent from the legally authorised representative. If no such representative is available and if the research cannot be delayed, the study may proceed without informed consent provided that the specific reasons for involving subjects with a condition that renders them unable to give informed consent have been stated in the research protocol and the study has been approved by a research ethics committee. Consent to remain in the research must be obtained as soon as possible from the subject or a legally authorised representative.

31. The physician must fully inform the patient which aspects of their care are related to the research. The refusal of a patient to participate in a study or the patient's decision to withdraw from the study must never adversely affect the patient-physician relationship.

32. For medical research using identifiable human material or data, such as research on material or data contained in biobanks or similar repositories, physicians must seek informed consent for its collection, storage and/or reuse. There may be exceptional situations where consent would be impossible or impracticable to obtain for such research. In such situations the research may be done only after consideration and approval of a research ethics committee.

### **Use of Placebo**

33. The benefits, risks, burdens and effectiveness of a new intervention must be tested against those of the best proven intervention(s), except in the following circumstances:

Where no proven intervention exists, the use of placebo, or no intervention, is acceptable; or

Where for compelling and scientifically sound methodological reasons the use of any intervention less effective than the best proven one, the use of placebo, or no intervention is necessary to determine the efficacy or safety of an intervention and the patients who receive any intervention less effective than the best proven one, placebo, or no intervention will not be subject to additional risks of serious or irreversible harm as a result of not receiving the best proven intervention.

Extreme care must be taken to avoid abuse of this option.

### **Post-Trial Provisions**

34. In advance of a clinical trial, sponsors, researchers and host country governments should make provisions for post-trial access for all participants who still need an intervention identified as beneficial in the trial. This information must also be disclosed to participants during the informed consent process.

### **Research Registration and Publication and Dissemination of Results**

35. Every research study involving human subjects must be registered in a publicly accessible database before recruitment of the first subject.

36. Researchers, authors, sponsors, editors and publishers all have ethical obligations with regard to the publication and dissemination of the results of research. Researchers have a duty to make publicly available the results of their research on human subjects and are accountable for the completeness and accuracy of their reports. All parties should adhere to accepted guidelines for ethical reporting. Negative and inconclusive as well as positive results must be published or otherwise made publicly available. Sources of funding, institutional affiliations and conflicts of interest must be declared in the publication. Reports of research not in accordance with the principles of this Declaration should not be accepted for publication.

### **Unproven Interventions in Clinical Practice**

37. In the treatment of an individual patient, where proven interventions do not exist or other known interventions have been ineffective, the physician, after seeking expert advice, with informed consent from the patient or a legally authorized representative, may use an unproven intervention if in the physician's judgement it offers hope of saving life, re-establishing health or alleviating suffering. This intervention should subsequently be made

the object of research, designed to evaluate its safety and efficacy. In all cases, new information must be recorded and, where appropriate, made publicly available.

12.1 Tables and graphs templates	
12.2 List of Tables, Graphs and Listings	

CER-001-CLIN-009

List of abbreviations and specialized terms:

AE	Adverse Event
ANCOVA	ANalysis of COVAriance
ATC	Anatomic Therapeutic Class
вмі	Body Mass Index
CI	Confidence Interval
CRF	Case Report Form
CRO	Contract Research Organization
DSMB	Data and Safety Monitoring Board
FPFV	First Patient First Visit
HLGT	Highest Level Group Terms
HLT	Highest Level Terms
ICH	International Conference on Harmonisation
LOCF	Last Observation Carried Forward
LPFV	Last Patient First Visit
LPLV	Last Patient Last Visit
MedDRA	Medical Dictionary for Regulatory Activities
МІ	Multiple Imputation
mITT	modified Intention-To-Treat
MRI	Magnetic Resonance Imaging
MVWA	Mean Vessel Wall Area
MVWV	Mean Vessel Wall Volume
PP	Per Protocol
PT	Preferred Term
Q1	1 st quartile
Q3	3 rd quartile
SAE	Serious Adverse Event
SAP	Statistical Analysis Plan
SOC	System Organ Class
SOP	Standard Operating Procedure
TBR	Target to Background Ratio
TFL	Tables Figures Listings
WHO-DD	World Health Organisation Drug Dictionary

CER-001-CLIN-009 CER-001

Introduction

The Statistical Analysis Plan (SAP) was developed from the following documents:

- Protocol (version 3.0 dated 13DEC2016)
- Case Report Form (CRF, version 18.2 on 30MAY2017)
- The International Conference on Harmonization (ICH) topics E3 (July 1996) [1] and E9 (September 1998) [2].

Analyses described throughout this document were planned before database lock. All analysis decisions were made prior to unblinding as well.

This SAP supersedes the protocol. Changes to the protocol (if any) will be reported in section *10 Modifications with respect to the protocol*. Finally, additional analyses not planned in this document should be clearly mentioned in the appropriate section of the clinical study report.

1. Study objectives

1.1 Primary objectives

The primary objectives of the study are:

- To evaluate the effect of 24 week treatment with CER-001 on carotid Mean Vessel Wall Area (MVWA) as compared to placebo using 3T Magnetic Resonance Imaging (3T-MRI);
- To evaluate the safety and tolerability of CER-001 administered for 24 weeks.

1.2 Secondary objectives

The secondary objectives of the study are:

- To evaluate the effect of 8 week and 48 week treatment with CER-001 on carotid artery MVWA as compared to placebo using 3T-MRI;
- To evaluate the effect of 8 week, 24 week and 48 week treatment with CER-001 on femoral artery MVWA as compared to placebo using 3T-MRI;
- To evaluate the effect of 24 week treatment with CER-001 in the target (plaque) to background (blood) ratio (TBR) from an index vessel (either right carotid or left carotid) based on the standardized ¹⁸FDG uptake measured with PET/CT.
- To evaluate safety and tolerability of 48 week treatment with CER-001.

1.3 Exploratory objectives

[figure not shown]
The exploratory objectives of the study are:

- To evaluate the effect of treatment with CER-001 with respect to other efficacy measurements including carotid artery and carotid normalized wall index using 3T-MRI;
- To evaluate the effect of treatment with CER-001 with respect to potential surrogate markers on vessel wall biology including laboratory variables;
- To evaluate the effect of treatment with CER-001 with respect to inflammation;
- To evaluate plasma-mediated cellular Cholesterol efflux capacity;
- To measure ApoA-1 levels (pharmacokinetic parameters);
- To measure Cholesterols, triglycerides, lipids, apolipoprotein and lipoprotein levels (pharmacodynamics parameters).

2. Study summary

This is a phase III, multi-centre, randomized, 48 weeks, double-blind, parallel-group, placebo-controlled study to evaluate efficacy and safety of CER-001 on ApoA-1 and vessel wall area in patients with genetically defined familial primary hypoalphalipoproteinemia and receiving background optimized lipid therapy.

The study design is illustrated in the following figure:

3. Sample size

The assumptions upon which the power calculations are based are data from the 7 patients completing the CER-001-CLIN-007 SAMBA study, given the similarity of the genetic mutations. Those patients presented with a median value for MVWA of 25.0 mm² and had a follow-up median value at 6 months of 21.8 mm². The mean percent reduction is reported as 6.7%, standard deviation = 4.5%. These observed values would provide a conservative estimate of the effect of CER-001 in the more severe population for this FPHA study.

Using these results from SAMBA (i.e. an assumed standard deviation of 4.5%) and a 2:1 randomization scheme to maximize exposure to active drug, 16 completing patients in the CER-001 group and 8 in the placebo group (24 total completers for mITT) would yield 90% power to detect a difference from baseline versus placebo of 6.7%, using two-tailed testing with α =0.05. A total of 30 patients are planned to be randomized that would provide a buffer such that a 20% discontinuation rate would still allow the study to retain sufficient power for a supporting per protocol efficacy analysis (MVWA).

CER-001-CLIN-009 CER-001

4. Randomization

After obtaining written informed consent, completing screening procedures, and ensuring the patient meets all of the inclusion criteria and none of the exclusion, the patient will be randomized. Stratification according to the genetic mutation (ABCA-1/ApoA-1) will be done to ensure appropriate balanced distribution of the mutations across treatment groups. The patient will be randomized to receive 29 infusions of either active drug or placebo using a 2:1 randomization scheme.

5. Unblinding

Unblinding will be performed by the ICTA PM statistician in charge of the study once database is locked, at the end of the study, with sponsor's agreement.

The unblinding process will be conducted according to ICTA SOP46 ("Randomization and unblinding"). ICTA Quality Assurance department will give the CD-Rom containing the randomization number and the corresponding randomization treatment to the statistician. The database will then be imported in the statistical database of the study. A 100% review of the imported data will be performed by the statistician, compared to initial data provided in the CD-Rom.

6. Populations to be analysed

6.1 Analysis populations of patients

The statistical analysis will be based on the three populations defined below. To be part of a population, patients should have signed informed consent and fullfill all inclusion / exclusion criteria. Some criteria have been added after the start of the study. Hence patients included before will be considered as compliant to these criteria via a Not Applicable (NA) status.

Safety population

The safety population will comprise all randomized patients who received at least one dose of study medication.

Safety analysis will be performed on the safety population according to the actual treatment received.

Modified Intent-To-Treat (mITT) population

The mITT population will comprise all randomized patients for whom at least one of the following conditions is satisfied:

- 3T-MRI assessment available at baseline (W0) and at least one post-baseline 3T-MRI assessment available
- 18FDG-PET/CT assessment available at baseline (W0) and at least one post-baseline 18FDG-PET/CT assessment available

Per Protocol (PP) population

The PP population will comprise all patients of the mITT population without any major protocol deviations (*Cf.* section 6.3).

Defining study populations and excluding patients from the analysis will be a joint decision taken by Sponsor and ICTA PM' representatives (Statistician and Project Leader). Patients to be excluded and

CER-001-CLIN-009 CER-001

reasons for their exclusion will be discussed during data review meetings, before database lock and unblinding.

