## **12.5 Populations for Analysis**

The objectives of this study will be addressed primarily through the modified Intention-to-Treat (mITT) approach. In this approach all randomized patients with at least one valid, post randomization efficacy measurement, i.e., a follow up evaluation, will be included in the efficacy assessments, irrespective of their protocol adherence. Additionally, a per-protocol analysis will be performed which will only include patients who received all infusions of study drug (up to the time of each analysis), at the planned dosage and have no major protocol violations. Documentation of patients included / excluded from analysis populations will be completed before the study is unblinded.

For safety evaluations, all randomized patients who received at least one dose of study medication will be included.

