6.2 Protocol deviations

A list of protocol deviations has been written by ICTA PM and sent to the sponsor for approval. The list contains possible protocol deviations (according to inclusion/exclusion criteria, disallowed treatments, minimum treatment exposure, and calendar of visits...), and significant deviations which require immediate information to the Sponsor. This list may be updated in the course of the data management process, and will be finalized during the data review meetings before database lock and unblinding.

TANGO_DeviationsLi

During the data review, the impact of each deviation (minor/major) on the primary endpoint will be discussed and thus, the list of patients to be excluded from the PP population will be defined.

Number and percentage of patients with at least one deviation, at least one major deviation, at least one deviation by type (Entry criteria / Study procedures / Investigational medicinal product) will be described. Each deviation will also be summarized by the number and percentage of patients who experienced it.

6.3 Disposition of patients

The following data will be described:

- Number of screened patients [a]
- Number of screening failures and reasons for screening failures
- Number of randomized patients grouped by treatment
- Number of patients for whom the blind was broken
- Number of patients with ABCA-1, ApoA-1 or both mutations
- Number of patients who did not receive any medication and reason for non-treatment
- Number of patients who received double-blind medication
- Treatment actually received (CER-001/Placebo)
- Number of patients who completed the study
- Number of premature discontinuations of the study treatment and reason for premature discontinuation (at each visit, and overall)
- Number of premature withdrawals and reason for premature withdrawal (at each visit, and overall)
- Number of patients who completed the induction period grouped by treatment (visit at W8 performed)
- Number of patients who completed the maintenance period grouped by treatment (visit at W24 performed)
- Number of patients who completed the extension period grouped by treatment (visit at W48 performed)
- Patient's follow-up duration
- Inclusion date of the first patient (FPFV: First Patient First Visit), date of first visit of the last patient (LPFV) and last visit date of the last patient (LPLV: Last Patient Last Visit)
- Number of patients in each analysis set and reasons for exclusion from the analysis sets

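### SAP 6.1 makes eligibility a condition of every analysis population, including Safety and mITT, against its own definitions, SAP 6.2 and protocol 12.5, and section 10 does not declare it

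*SAP*

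**What the plan says.** SAP 6.1 announces three populations (Safety, mITT, PP) and then sets a general condition: "To be part of a population, patients should have signed informed consent and fullfill all inclusion / exclusion criteria". Because some criteria were added after the study started, it adds a waiver for patients who entered earlier: "Hence patients included before will be considered as compliant to these criteria via a Not Applicable (NA) status".

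The definitions that follow contain no eligibility condition for the first two sets. For Safety: "The safety population will comprise all randomized patients who received at least one dose of study medication". For mITT: "The mITT population will comprise all randomized patients for whom at least one of the following conditions is satisfied", the conditions being a baseline plus at least one later 3T-MRI, or the same for PET/CT. PP is mITT without major deviations.

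SAP 6.2 lists breaches of entry criteria among the possible protocol deviations. They are to be counted: "at least one deviation by type (Entry criteria / Study procedures / Investigational medicinal product) will be described". Each deviation is graded minor or major for its impact on the primary endpoint, and from this "the list of patients to be excluded from the PP population will be defined". No other population is named there.

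Protocol 12.5 says that randomized patients with a valid follow-up efficacy measurement "will be included in the efficacy assessments, irrespective of their protocol adherence", and it bases safety on all randomized patients with at least one dose.

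The SAP Introduction gives the SAP precedence over the protocol and says that changes are reported in section 10. Section 10 reports only the replacement of ANCOVA by a repeated-measures mixed model.

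**The concern.** A patient can be randomized, dosed and imaged, and only later be found to have breached an entry criterion. The general sentence in SAP 6.1 would remove that patient from all three sets; the definitions below it would keep the patient in Safety and mITT.

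Two things are at stake. First, SAP 7.5 runs every safety analysis on the Safety population, so the patient would be missing from the adverse event, laboratory and ECG summaries. Safety and tolerability over 24 weeks is one of the two primary objectives. Second, SAP 7.4.1.1 fits the primary model to mITT, so the primary estimate would lose a patient whom the protocol says to keep.

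If the restriction is intended, it changes the protocol's populations without being declared. If it is not intended, it is a drafting error in the document that takes precedence.

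**Working it through.** **Texts side by side: a dosed patient with imaging who breached an applicable entry criterion**

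| Source | Safety | mITT | PP |
|---|---|---|---|
| SAP 6.1, general sentence | out | out | out |
| SAP 6.1, definitions | in | in | depends on major deviation |
| SAP 6.2 | exclusion not mentioned | exclusion not mentioned | out if listed after grading |
| Protocol 12.5 | in | in | out if a major violation |

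The general sentence is not idle wording. The waiver for criteria added later is needed only if unmet criteria would otherwise count against a patient. It covers only those criteria; all others still bind.

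The general sentence also defeats the grading in SAP 6.2. A patient with a minor entry-criteria deviation would stay in PP under 6.2, but under 6.1 has already left mITT, of which PP is a subset. Grading that deviation would then have no effect.

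SAP section 10 contains no change to the populations.

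**Size, primary analysis.** Inputs from SAP section 3 (the same as protocol 12.4): difference 6.7%, SD 4.5%, two-sided alpha 0.05, 16 and 8 completers, 30 randomized 2:1. The formula is two-sample t-test power with df = n1 + n2 − 2 and noncentrality 6.7 / (4.5 × √(1/n1 + 1/n2)).

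The plan's figure first: at 16:8, df = 22, noncentrality 3.438, critical t 2.074, power 90.7%. This agrees with the stated 90%.

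Now remove one patient:

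| Set | Noncentrality | Power |
|---|---|---|
| 16:8 | 3.438 | 90.7% |
| 15:8 (one CER-001 patient out) | 3.401 | 90.0% |
| 16:7 (one placebo patient out) | 3.286 | 87.9% |
| 20:10 | 3.844 | 96.0% |
| 19:10 (one CER-001 patient out) | 3.811 | 95.7% |
| 20:9 (one placebo patient out) | 3.709 | 94.7% |

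The 20:10 rows are shown because mITT does not require completion, so the set may exceed 24. These figures are indicative only: they come from a t-test on percent change, while the main analysis is a mixed model on change in mm².

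**Size, safety tables.** Assume that all 20 CER-001 patients are dosed, one is excluded as ineligible, and that patient alone had a given adverse event. Exact one-sided 95% upper bounds:

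- Patient kept: 1/20 = 5%; upper bound is the 0.95 quantile of Beta(2, 19) = 21.6%.
- Patient dropped: 0/19 = 0%; upper bound 1 − 0.05^(1/19) = 14.6%.

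**The case against.** The strongest reply is that a specific text overrides a general one. The Safety and mITT definitions are specific and say who will be included; the opening sentence is general and says only what patients should satisfy. On that reading there is no eligibility filter on Safety or mITT, SAP 6.2 fits, and section 10 has no such change to declare. Section 10 is also silent on other population differences, such as the baseline imaging that the SAP requires for mITT and the protocol does not, so its silence proves little about intent. Exclusions are a joint decision of sponsor and CRO at data review, before lock and unblinding, not an automatic step. Eligibility is confirmed before randomization, so perhaps nobody is affected. An excluded patient would still appear in the baseline tables and individual listings, and SAP 6.3 reports "Number of patients in each analysis set and reasons for exclusion from the analysis sets". The deviation list embedded in SAP 6.2 is not visible and might settle the matter.

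Much of this limits the consequence, and that part stands. It does not remove the contradiction. Preferring the specific definitions means setting aside a sentence that the waiver shows was meant to operate. Leaving the choice to data review means deciding between two incompatible rules case by case. The SAP also plans to count entry-criteria deviations, so it allows for ineligible patients among those randomized. A listing does not put a dosed patient back into the safety tables.

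**Conclusion.** The concern holds, as a point that should be fixed. Followed literally, SAP 6.1 excludes dosed but ineligible patients from Safety and evaluable but ineligible patients from mITT. This conflicts with its own definitions, with SAP 6.2 and with protocol 12.5, and it is not declared in section 10. Confidence is high for the contradiction in the running text. Whether any patient would be dropped is not known.

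The likely effect on the primary analysis is small: for one excluded patient, 0.7 or 2.8 percentage points of power from 16:8, and 0.3 or 1.3 points from 20:10 (CER-001 or placebo patient respectively). The safety tables are the more serious side, because with about 20 treated patients a single exclusion can remove an event from the summary altogether. The decision before unblinding limits bias but does not resolve the conflict.

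**What to change.** - In SAP 6.1, end the general sentence after the consent requirement.
- State that Safety (randomized, at least one dose) and mITT (randomized, with the stated imaging) apply regardless of eligibility deviations.
- Apply eligibility to PP only, through the major-deviation review in SAP 6.2.
- Move the two sentences on later-added criteria to that rule, so that patients who entered earlier are not counted as deviating.
- Correct the cross-references: the PP definition should cite 6.2, not 6.3; SAP 7.1.3 should cite 7.4, not 7.5; SAP 7.1.5 cites a section 6.4 that does not exist.

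If the sponsor does want the restriction, it must instead be declared and justified in section 10.

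The cost is a text edit to SAP 6.1 and 6.2 before unblinding, with no new data and no new programming method. Its downside is that ineligible patients kept in mITT may slightly dilute the treatment effect; the planned PP analysis already addresses that. The baseline-imaging difference between the SAP and protocol definitions of mITT is a separate matter, which this edit does not settle.
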